Number of patients Number planned (Statistical design)	
The trial is primarily intended to show superiority but it is also powered to enable a second primary conclusion of non-inferiority using pre-specified hypotheses on the acceptable non-inferiority margin.
 
The sample size calculation uses the following assumptions:
 
 
◆ The patient accrual rate reaches a steady state of 300 patients per year from year 2 of recruitment onwards. During the first year, the yearly accrual rate is assumed to gradually increase quarterly from 76 patients/year (months 1-3), to 124 pts/year (months 4-6), to 174 patients / year (months 7-9), to 227 patients / year (months 10-12).
 
◆ The cumulative rate of patients loss to follow-up is 5% at year 5
 
◆ The trial-level type I error rate is 0.025 1-sided
 
◆ Based on an (unpublished) reanalysis of the data from the 3-year hormone-deprivation therapy arm of EORTC trial 22961, restricted to the subset of patients that had a baseline PSA>10 ng/ml and at least 2 risk factors as specified in the eligibility criteria of the present study, the 5-year progression-free survival rate was 68.7% (95% CI: 62.9%-73.7%). The sample size is thus based on the assumption that the 5-year progression-free survival rate in the comparator arm of this study is 68.5%
 
 
The hypothesis test of superiority of the experimental treatment arm for the primary endpoint progression-free survival is

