	
<math>H_{0\text{superiority}} : HR \geq 1</math> versus <math>H_{1\text{superiority}} : HR < 1</math>
 
The study is sized to have 80% power to reject <math>H_{0\text{superiority}}</math> under the alternative that the true benefit amounts <math>HR=0.708</math> (i.e. +8% at 5 years from anticipated 68.5% at 5 years in the reference arm).
 
The non-inferiority boundary is set at <math>HR=1.159</math> and corresponds to the non-inferiority test
 
<math>H_{0\text{non-inferiority}} : HR \geq 1.159</math> versus <math>H_{1\text{non-inferiority}} : HR < 1.159</math> (i.e. -4% at 5 years)
 
We note that <math>H_{1\text{non-inferiority}}</math> is included in <math>H_{1\text{superiority}}</math>. This justified the closed-testing argument below.
 
With the above specifications, the superiority test requires observing a total of 264 events for the primary endpoint. It is also estimated that with 885 patients entering the study in 3.45 years will provide this number of events, if the total study duration is 7.7 years (i.e. with 4.2 years of follow-up after the entry of the last patient).
 
With this number of events, the study will also have 80% power of rejecting the null hypothesis of inferiority (<math>H_{0\text{non-inferiority}} : HR \geq 1.159</math>) under the alternative assumption of a marginal treatment benefit in favor of the experimental arm amounting <math>HR=0.821</math> (+4.8% at 5 years), using the 1-sided type I error rate of 0.025. By the closed-testing principle, this strategy guarantees strict control of the trial type I error.

Number analyzed	885

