
Diagnosis and main criteria for Inclusion
	
Inclusion criteria
 
 
◆ Histologically confirmed diagnosis of prostate adenocarcinoma
 
◆ PSA <math>\geq 10</math> ng/ml and two of the following 4 criteria: 
 
◆ PSA <math>\geq 20</math> ng/ml,
 
◆ Gleason sum <math>\geq 8</math>,
 
◆ cN1 (regional LN with a short axis length <math>>10</math>mm by CT scan or MRI) or pathologically confirmed lymph nodes (pN1) (see Appendix H),
 
◆ cT3-T4 (by MRI or core biopsy)
 
 
 
 
(i.e. If PSA <math>\geq 20</math> ng/ml then only one of the other 3 risk factors is needed)
 
 
◆ M0 by standard imaging work-up (see chapter 6.1.1.1)
 
◆ Testosterone <math>\geq 200</math> ng/dl
 
◆ Adequate renal function: calculated creatinine clearance <math>\geq 50</math> mL/min (Appendix D) Magnesium and potassium within normal limits of the institution or corrected to within normal limits prior to the first dose of treatment.
 
◆ Patients with prolonged QT-intervals due to prescribed Class IA (quinidine, procainamide) or Class III (amiodarone, sotalol) antiarrhythmic medication must be carefully evaluated for GnRH-
 

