Statistical methods	
 
◆ Treatment allocation method: No blinding is applied in this study. Before the start of the hormonal therapy, the patients are allocated between the two treatment groups in a 1:1 ratio, by means of stratified blocked randomization with variable block sizes. Stratification factors will be the presence of previous clinical cardiovascular event (no vs yes), the country where the patient is treated, and the number of high risk factors that the patient presents (2 vs >2 high risk factors of relapse)
 
◆ Analysis populations 
 
◆ Intention-to-treat population: All randomized patients will be analyzed in the arm they were allocated by randomization.
 
◆ Per protocol population 1: All patients who are eligible and have received at least 6 months of the allocated treatment
 
◆ Safety population: All patients who have started their allocated treatment (at least one injection of the allocated treatment)
 
◆ Per protocol population 2 (adjusted for switch): All patients who are eligible and have started treatment censoring observations at the time of switching treatment (from GnRH-antagonist to GnRH-agonist) or stopping treatment in absence of progression.
 
 
 
 
Analysis methods:
 
 
◆ The primary analysis of the primary endpoint will be performed in the intent-to-treat population for the superiority test. Two sensitivity analyses will be conducted, repeating the test in the per protocol population 1 and in the per protocol population 2.
 
◆ If the superiority test fails to reject the null hypothesis of no difference a non-inferiority test will be conducted. To protect against the risk of false positive conclusions, the primary test for the non-inferiority question will be conducted in the in the per protocol population 2. The test in the intention-to-treat population and in the per-protocol population 1 will be performed as a first sensitivity analysis. A second sensitivity analysis will be conducted in intent-to-treat population.
 

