	
 
◆ All secondary efficacy endpoints will be reported in the intent-to-treat population. A sensitivity analysis of the endpoint PSA at 6 months will also be conducted in the per protocol population
 
◆ Safety will be reported in the per protocol population 2 and in the safety population.
 
◆ Quality-of-life and other patient reported outcomes will be reported in the intent-to-treat population
 
◆ Testing strategy for the primary endpoint:  
The 2-sided 95% confidence interval for the hazard ratio for the treatment effect on the primary trial endpoint will be calculated based on a Cox regression model stratified for the stratification factors of the randomization.
 
The test for superiority is conducted first. If it does reject the null hypothesis of no difference (one-sided <math>P < 0.025</math>) then one concludes to superiority of the GnRH-antagonist.
 
If one does not, then the primary test for the non-inferiority question is conducted. If the upper bound of the 2-sided 95% confidence interval around the HR (agonist/antagonist) is <math>< 1.159</math> then one concludes to non-inferiority.
 
Otherwise, one concludes that neither non-inferiority nor superiority of the experimental treatment can be demonstrated compared to the standard treatment.
 
This strategy guarantees full control over the type I error rate of the trial.
 
 
◆ Analysis of secondary endpoints  
The secondary endpoint clinical progression-free survival is also assessed by means of cox regression stratified by the stratification factors of the randomization.
 
The secondary endpoints time to time to next systemic anticancer therapy (including secondary hormonal manipulation) and cancer specific survival are analyzed by means of a Fine-and-Gray model stratified by the stratification factors of the randomization.
 
Quality of life endpoints are analyzed by means of mixed effects regression models adjusted for the stratified by the stratification factors of the randomization. I-PSS scores over time will be reported as change scores from baseline. Health Economic analysis will be done using the scores from the EQ-5D-5L tool (Ref. 39)
 
The other secondary endpoints as well as the main safety endpoints are compared by means of logistic regression models stratified by the stratification factors of the randomization.
 
Other safety parameters are described as frequency tables.
 
 
◆ Interim monitoring
 
◆ No formal interim stopping rule based on efficacy is planned in this study. The central IDMC for the EORTC studies will review the trial at
 

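### The primary Cox model is valid, but adding PSA, Gleason sum, nodal status and T category as pre-specified covariates is a cheap gain of about 0 to 4 points of power

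*Protocol*

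**What the plan says.** All references are to the Protocol summary.

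- **Primary model** (Statistical methods, testing strategy for the primary endpoint): the hazard ratio and its two-sided 95% interval are "based on a Cox regression model stratified for the stratification factors of the randomization". No other covariate is named.
- **Stratification factors** (treatment allocation method): previous clinical cardiovascular event, country, and "the number of high risk factors that the patient presents", split as 2 versus more than 2.
- **Baseline disease variables** (inclusion criteria): entry requires PSA of at least 10 ng/ml and two of four features, namely PSA of at least 20, Gleason sum of at least 8, nodal involvement, and "cT3-T4 (by MRI or core biopsy)".
- **Sizing** (statistical design): "The trial-level type I error rate is 0.025 1-sided"; "the superiority test requires observing a total of 264 events for the primary endpoint"; the target effect is a gain of "8% at 5 years from anticipated 68.5% at 5 years in the reference arm", expressed as HR 0.708. The non-inferiority margin is HR 1.159, a loss of 4 points at 5 years.
- **Non-inferiority population** (analysis populations and methods): the primary non-inferiority test is in per protocol population 2, which censors at a switch from antagonist to agonist or at stopping treatment without progression.

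**The concern.** A count cut at 2 versus more than 2 discards information. Two men with quite different disease, for example PSA 20 with T3 and node-positive with Gleason 10, can share a stratum. PSA contributes only through the cut at 20. If these variables predict progression within the count groups, leaving them out of a Cox model pulls the estimated hazard ratio toward 1 and costs some power. The design has no slack, at almost exactly 80% for both tests.

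The non-inferiority test gives a second reason. Censoring at a switch applies to one arm only, so randomization no longer fully protects that comparison. If switching depends on baseline disease risk, a model that carries more of that risk is less biased.

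The primary model is named in this protocol, so changing it is not a detail that a separate analysis plan could settle without departing from the protocol.

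**Working it through.** **1. The protocol's figures.** Inputs from the statistical design: one-sided 0.025, 80% power, HR 0.708, 1:1 allocation.

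- Effect: ln(0.765)/ln(0.685) = 0.708. Margin: ln(0.645)/ln(0.685) = 1.159. Both come from marginal 5-year rates.
- Events (Schoenfeld): 4 × (1.960 + 0.842)² / ln(0.708)² = 4 × 7.849 / 0.1192 = 263.3, so 264, as stated.
- Superiority power: Φ(√264/2 × 0.3453 − 1.960) = 80.1%.
- Non-inferiority power at HR 0.821: Φ(√264/2 × ln(1.159/0.821) − 1.960) = 80.0%.
- Stated accrual, exponential times and 5% loss give 265 expected events from 885 patients at 7.7 years.

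None of this depends on covariate adjustment.

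**2. Power with the four covariates added.** The documents give no prognostic effects, factor prevalences or number of countries, so all of these are assumed.

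Simulation A: 6,000 trials per scenario; prevalences before selection of PSA ≥20 60%, Gleason ≥8 60%, N1 25%, T3-4 75%; prior cardiovascular event 20%; 12 countries. Assumed HRs per factor: moderate 1.35-1.5, strong 1.65-2.0, very strong 2.0-2.5. Continuous PSA per SD: 1.22 in the strong scenario and 1.5 in the very strong one. *Marginal* sets treated-arm 5-year PFS at 76.5%, as the protocol does. *Conditional* sets the covariate-adjusted HR at 0.708.

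Simulation B: 2,500 trials per scenario, conditional HR 0.708. Assumed HRs per PSA doubling / Gleason ≥8 / N1 / T3-4: 1.2/1.5/1.7/1.3, 1.3/2.0/2.2/1.5 and 1.5/2.5/2.8/1.8.

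Simulation C: a separate run of 2,500 trials per scenario, conditional HR 0.708.

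Superiority power (%), planned → adjusted:

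| Prognostic strength | A, marginal | A, conditional | B | C |
|---|---|---|---|---|
| None | 78.9 → 78.7 | 78.9 → 78.7 | not run | 77.2 → 77.3 |
| Moderate | 79.3 → 79.4 | 78.6 → 78.5 | 78.6 → 79.2 | 76.8 → 77.6 |
| Strong | 80.3 → 81.1 | 77.6 → 78.2 | 76.0 → 77.8 | 75.8 → 78.1 |
| Very strong | 80.3 → 83.3 | 73.4 → 77.7 | 74.2 → 78.2 | 73.2 → 77.2 |

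Moderate effects plus continuous PSA (1.22 per SD) in A gained 0.9 (marginal) and 0.4 (conditional). Under the marginal calibration, C gained −0.1 to +2.7. A further 2,000 trials per scenario with B's HRs gained 0.0, 2.0 and 5.3. The Monte Carlo standard error of each power is about 0.5 points in A and 0.9 elsewhere.

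Across all runs the change is −0.2 to +2.3 points for none to strong effects. For very strong effects, single estimates run from 2.7 to 5.3 and centre on 3 to 4. In A, stratifying over 12 assumed countries itself costs about 1.3 points, so not every shortfall from 80% comes from omitted covariates.

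**3. Chance imbalance.** The SD of imbalance on the log HR is 2/√885 × residual SD of risk within the count groups. For residual SDs of 0.23 and 0.47 this is 0.015 and 0.032, against a standard error of 2/√264 = 0.123. A 1.96-SD imbalance moves the HR by about 3% to 6%.

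**4. Non-inferiority in per protocol population 2.** An illustration assumes that about 25% of antagonist patients switch within 2 years, more often at higher risk (log-odds 0.5 or 1.0 per SD), with a true conditional HR of 1.159. The false non-inferiority rate, nominally 2.5%, is 3.8-5.1% with the planned model and 2.4-3.1% with the four covariates (standard error about 0.4 points). A small part of the difference is attenuation of the unadjusted HR, not censoring bias.

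**5. The margin on the adjusted scale.** In A, the conditional HR matching a marginal 0.708 is 0.706 (moderate), 0.698 (strong) or 0.686 (very strong). Scaling the log margin by the same ratio, for example ln(0.686)/ln(0.708) = 1.091, turns 1.159 into about 1.160, 1.166 and 1.175. Holding the adjusted HR to 1.159 is therefore slightly stricter.

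**The case against.** The strongest reply is that nothing here is wrong. A Cox model stratified by the randomization factors is valid and matches the allocation. Under the protocol's own marginal definition of the effect, simulation A gives the planned model 78.9% to 80.3% in every scenario, so adjustment adds to roughly the designed power and does not repair a shortfall. The larger apparent losses appear when 0.708 is read as a conditional HR, which the protocol does not do. All of this stands.

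It also stands that the top of the range needs very strong predictors, that the margin was set on marginal rates, and that complete recording of all four variables is inferred: the higher-count stratum can be assigned once three features are met, so the fourth could be missing.

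A supportive adjusted analysis could be left to the statistical analysis plan. That answers less, because the proposal concerns the primary model, which this protocol already fixes.

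A reader might infer three stronger things. One is that the trial is underpowered by 4 points; the documents give no prognostic strengths to support that. Another is that chance imbalance invalidates the comparison; it is random, small against the standard error, and already within the type I error rate. The third is that the non-inferiority error rate is inflated; the protocol says nothing about who will switch, and the opposite pattern would bias against the antagonist.

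**Conclusion.** This is an inexpensive improvement, not a defect. The intention-to-treat superiority analysis is valid as written. Its only disease-risk term is coarse, while finer baseline information is assessed for eligibility. Adjustment would be expected to add about 0 to 2 points of superiority power if the four variables have no to strong prognostic effect within the count groups, and about 3 to 4 points only if the effects are very strong. These figures rest on assumed prognostic HRs, prevalences and 12 countries. For non-inferiority the benefit is lower bias if switching or stopping depends on baseline risk. Its direction and size cannot be fixed from the documents.

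**What to change.** In the testing strategy for the primary endpoint:

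1. Keep the stratified Cox model and add four pre-specified covariates to the primary superiority model: log PSA, Gleason sum, N (N0 versus N1) and T (T1-2 versus T3-4). Report the stratified-only model as a sensitivity analysis.
2. For non-inferiority in per protocol population 2, report the same adjusted model. State that 1.159 was derived from marginal 5-year rates (a loss of 4 points from 68.5%) and that applying it unchanged to the adjusted HR is slightly stricter.
3. Add a simple rule, fixed in advance, for any missing covariate value.

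The cost is a few sentences and no new assessments, provided the four baseline values are recorded. The downside is that the HR becomes conditional on four more factors, which the report should say.

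### The non-inferiority decision rule names the hazard ratio as agonist/antagonist, the reciprocal of the ratio on which the 1.159 margin was set, so followed literally it reverses the decision

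*Protocol*

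**What the plan says.** The statistical design (Protocol summary, Number of patients) takes the GnRH agonist as reference and assumes that "the 5-year progression-free survival rate in the comparator arm of this study is 68.5" percent. The superiority alternative is a hazard ratio of 0.708, explained as "i.e. +8% at 5 years from anticipated 68.5% at 5 years in the reference arm". The non-inferiority null hypothesis is a ratio of 1.159 or more, explained as a loss of 4 points at 5 years. Power for non-inferiority is given as 80% at a ratio of 0.821, "under the alternative assumption of a marginal treatment benefit in favor of the experimental arm amounting" to 4.8 points at 5 years. In each case a ratio below 1 is good for the antagonist.

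The decision rule (Protocol summary, Statistical methods, testing strategy for the primary endpoint) tests superiority first. If that fails, non-inferiority is concluded on this condition: "If the upper bound of the 2-sided 95% confidence interval around the HR (agonist/antagonist) is" below 1.159. The same section then states that the strategy fully controls the type I error rate.

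**The concern.** The rule places the control drug in the numerator, whereas the design places the experimental drug there. Inverting a hazard ratio means that the margin and the relevant confidence limit must change too. An upper limit of 1.159 on antagonist/agonist corresponds to a lower limit of 1/1.159 = 0.863 on agonist/antagonist. The rule inverts the ratio but keeps both the number and the upper bound.

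On the ratio as labelled, a harmful antagonist gives values below 1 and tends to satisfy the condition, while a modestly helpful one gives values above 1 and tends to fail it. The sentence governs a confirmatory conclusion, and it is the only place where the protocol states the orientation of the ratio by drug name. An inferior antagonist fails superiority and so goes straight to this step. Testing superiority first therefore gives no protection against the false claim.

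**Working it through.** **Inputs, all from the Protocol summary.** Control 5-year progression-free survival 68.5%; one-sided type I error 0.025; 80% power; alternatives 0.708 (superiority) and 0.821 (non-inferiority); margin 1.159; 264 events; 1:1 allocation.

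**Step 1: the direction used in the design.** Under proportional hazards, HR (antagonist/agonist) = ln(S antagonist) / ln(S agonist):

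- +8 points: ln 0.765 / ln 0.685 = 0.708
- −4 points: ln 0.645 / ln 0.685 = 1.159
- +4.8 points: ln 0.733 / ln 0.685 = 0.821

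All three match the protocol. The reciprocals (1.412, 0.863, 1.218) appear nowhere in it.

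**Step 2: the design figures.**

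- Events for superiority (Schoenfeld): 4 × (1.960 + 0.842)² / (ln 0.708)² = 264 after rounding up, as stated.
- SE of ln HR: 2/√264 = 0.1231.
- Non-inferiority power: Φ[(ln 1.159 − ln 0.821)/0.1231 − 1.96] = 80.0%, as stated.

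The design is therefore consistent when the ratio is antagonist/agonist.

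**Step 3: where each rule passes.** With exp(1.96 × 0.1231) = 1.273, in terms of the observed antagonist/agonist ratio:

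- superiority: below 1/1.273 = 0.786
- intended non-inferiority: below 1.159/1.273 = 0.911
- rule as written: upper limit of the reciprocal below 1.159, which means a lower limit of antagonist/agonist above 0.863, hence an observed ratio above 1.273/1.159 = 1.098

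**Step 4: probability of passing the non-inferiority step,** taken alone with 264 events. For true antagonist/agonist ratio h, the intended rule gives Φ[ln(1.159/h)/0.1231 − 1.96]. The rule as written gives Φ[ln(1.159 × h)/0.1231 − 1.96].

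| True HR (antagonist/agonist) | Intended | As written |
|---|---|---|
| 0.821 | 80.0% | 0.9% |
| 1.00 | 22.3% | 22.3% |
| 1.159 | 2.5% | 66.9% |
| 1.30 | 0.2% | 91.5% |

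**Step 5: two possible results.**

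- Observed ratio 0.85 (95% CI 0.668 to 1.082): fails superiority and meets the intended non-inferiority rule. Inverted it is 1.176 (0.924 to 1.497) and fails the rule as written.
- Observed ratio 1.30 (1.021 to 1.655): the antagonist is significantly worse. Inverted it is 0.769 (0.604 to 0.979) and passes the rule as written.

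**The case against.** The strongest reply is that the intention is plain. The formal hypotheses, the three anchored hazard ratios and the rest of the testing strategy, which treats the antagonist as the experimental treatment, all point one way. One parenthesis conflicts with them. A statistician coding from the hypotheses would probably get it right, so this is most likely a drafting slip. That stands as an account of how it arose. It does not make the written rule correct.

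Three limits on the figures also stand:

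- **Order of testing.** A benefit large enough to win superiority (observed ratio below about 0.786) never reaches the faulty step. The beneficial results wrongly lost are those between about 0.786 and 0.911. At a true ratio of 0.821, superiority alone succeeds about 36.0% of the time. If both steps used the same data with 264 events, the chance of either favourable conclusion would be about 36.0% + 0.9% = 36.9%, against 80.0% as intended. The comparison of 0.9% with 80% is still like for like, because the protocol states its 80% for the non-inferiority test itself.
- **Not every worse antagonist passes.** The observed ratio must exceed about 1.098.
- **Number of events.** The primary non-inferiority test uses per protocol population 2, which censors at switching or stopping treatment without progression and may hold fewer than 264 events. With an assumed 200 or 150 events, the chance of passing at the margin under the rule as written is about 55% or 44%. Both remain far above 2.5%.

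**Conclusion.** The concern holds. The 1.159 margin is defined only for antagonist/agonist, and the decision rule applies it unchanged to the reciprocal. Followed literally, the non-inferiority step has a false-positive probability of 66.9% at the margin instead of 2.5%, and passes with probability 0.9% instead of 80% at its planning alternative. The claim of full type I error control then fails.

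These figures assume proportional hazards, 1:1 allocation, a normal approximation for ln HR and 264 events in the non-inferiority analysis. Fewer events change their size but not the direction of the error. The sample size, margin, error rate and hypotheses are unaffected. The correction is needed because the sentence is the prespecified rule for a primary conclusion in an open-label trial. Changing it after the data are seen would invite a dispute over whether the primary rule had been altered.

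**What to change.** In the testing strategy, replace the label in parentheses with HR (GnRH antagonist / GnRH agonist), keeping the upper bound and the 1.159 limit. State once, for both the superiority and the non-inferiority test, that a ratio below 1 favours the antagonist. This restores 80.0% power at 0.821 and 2.5% error at 1.159 under the stated design.

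The statistical analysis plan was not available for this review. If it repeats the rule, its orientation should be checked against the corrected wording. The cost is one phrase and one sentence in the protocol, with no effect on sample size, data collection or trial conduct.

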## Protocol summary

Title of the Study	Phase IIIb randomized trial comparing irradiation plus long term adjuvant androgen deprivation with GnRH antagonist versus GnRH agonist plus flare protection in patients with very high risk localized or locally advanced prostate cancer. A joint study of the EORTC ROG and EORTC GUCG.
Objective(s)	
The primary objective of the trial is to assess if GnRH antagonists in combination with external beam radiation therapy improve progression free survival (progression that can be biological, clinical, or death) compared to GnRH agonists in combination with external beam radiation therapy.
 
Secondary objectives include:
 
 
◆ documentation of effect of GnRH antagonists on clinically significant cardiovascular events in the subgroup of patients at high risk of such events at baseline;
 
◆ documentation of side effects and quality of life, I-PSS and urinary tract infections;
 
◆ assessment of relative treatment effect on secondary efficacy endpoints (clinical progression, time to next line of systemic therapy, time on therapy, overall and cancer specific survival) and on PSA at 6 months after end of RT.
 

Methodology	Phase IIIb randomized stratified open-label comparative 2-arm superiority study with a pre-set non-inferiority boundary.

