
Criteria for evaluation
 
Efficacy
 
Safety
	
The primary endpoint is progression-free survival defined as the time in days from randomization to death, clinical or biochemical progression, whichever comes first.
 
Where
 
 
◆ PSA progression based on Phoenix definition, i.e. a rise by 2 ng/mL or more above the nadir PSA (Ref. 17) confirmed by a second value measured minimum 3 months later
 
◆ Clinical progression is defined as onset of obstructive symptoms requiring local treatment and demonstrated to be caused by cancer progression or evidence of metastases detected by clinical symptoms and confirmed by imaging
 
◆ Start of another line of systemic therapy in absence of progression
 
◆ Death due to any cause
 
 
Secondary endpoints:
 
 
◆ Clinical progression-free survival
 
◆ Time to next systemic anticancer therapy (including secondary hormonal manipulation)
 
◆ Proportion of patients switching from GnRH antagonists to GnRH agonists and total effective duration of treatment with the originally allocated drug.
 
◆ Overall survival
 
◆ Cancer specific survival
 
◆ PSA at six months after completion of RT
 
 
Safety will be scored by the CTCAE version 4.0. The major safety endpoints in this study are
 
 
◆ the incidence of clinical cardiovascular events – CCE (i.e. arterial embolic or thrombotic events, hemorrhagic or ischemic cerebrovascular conditions, myocardial infarction, and other ischemic heart disease) in patients who had cardiovascular events before entering the trial and in those without such events.
 
◆ Incidence of urinary tract infection
 

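### By its catch-all clause, the protocol sends overall survival and duration on the allocated drug to logistic regression, which suits neither

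*Protocol*

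**What the plan says.** All references are to the Protocol summary.

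- **Objective(s)** lists among the secondary efficacy endpoints "time to next line of systemic therapy, time on therapy, overall and cancer specific survival".
- **Criteria for evaluation** repeats "Overall survival" as a secondary endpoint, with no fixed time point. It pairs the proportion switching from antagonist to agonist with the "total effective duration of treatment with the originally allocated drug". PSA six months after radiotherapy is also listed.
- **Statistical methods, analysis of secondary endpoints** assigns models in turn. First, "The secondary endpoint clinical progression-free survival is also assessed by means of cox regression stratified by the stratification factors of the randomization". Next, time to next systemic therapy "and cancer specific survival are analyzed by means of a Fine-and-Gray model". Quality of life gets mixed models and I-PSS is reported as change scores. Then comes the residual clause: "The other secondary endpoints as well as the main safety endpoints are compared by means of logistic regression models", stratified by the randomization factors.

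No sentence in the summary names a method for overall survival.

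**The concern.** A residual clause is still a rule. Once the named endpoints are removed, overall survival is among those left, so the protocol assigns it a method that has no place for censoring or follow-up time. This is different from leaving the method to the analysis plan: an analysis plan that used Cox regression for overall survival would depart from the protocol's text.

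Patients enter over several years and are analysed at one calendar date. With no landmark, the natural logistic outcome is dead or not dead by the cut-off. A patient lost alive in year 1 and a patient alive after 7.7 years then carry the same value. The comparison between arms depends on how long each arm was observed as well as on mortality. Duration on the allocated drug has a more basic problem: it is a length of time, and a logistic model cannot be fitted to it without a threshold that the protocol does not give.

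**Working it through.** **1. Which endpoints the residual clause catches**

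| Secondary efficacy endpoint | Method named |
|---|---|
| Clinical progression-free survival | Stratified Cox |
| Time to next systemic therapy | Fine-and-Gray |
| Cancer specific survival | Fine-and-Gray |
| Overall survival | None, so logistic |
| Switching; total duration on allocated drug | None, so logistic |
| PSA six months after radiotherapy | None, so logistic |

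**2. The plan's own design figures reproduce**

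- The inputs are HR 0.708, 80% power, 1:1 allocation, and the stated error rate: "The trial-level type I error rate is 0.025 1-sided".
- Events by Schoenfeld: 4 × (1.960 + 0.842)² / (ln 0.708)² = 263.3, rounded up to 264, as stated.
- Accrual: (76 + 124 + 174 + 227)/4 + 300 × 2.45 = 150.25 + 735 = 885.25, matching 885 in 3.45 years.

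The protocol gives no power or sample size for overall survival, so there is no such figure to reproduce.

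**3. How unequal follow-up is by design**

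- Shortest potential follow-up: 7.7 − 3.45 = 4.25 years (stated as 4.2). Longest: 7.7 years. Median: about 5.7 years.
- Patients entering after year 2.7 have under 5 years: 300 × (3.45 − 2.7) = 225, and 225/885.25 = 25%.
- Allowing for 5% loss at year 5 and an assumed 5-year survival of 80% to 90%, simulation puts 24% to 27% of all patients alive and censored before year 5.

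**4. Effect on the comparison, by formula**

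Assume exponential survival and exponential independent loss. For hazard λ, loss rate δ and follow-up F, the probability of an observed death is P = λ/(λ+δ) × [1 − exp(−(λ+δ)F)].

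Take no treatment effect, 5-year survival 85% (assumption) and F = 5.72 years:

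- λ = −ln(0.85)/5 = 0.0325.
- Loss 5% at year 5: δ = −ln(0.95)/5 = 0.0103, so P = 0.165.
- Loss 15% at year 5 (assumption): δ = −ln(0.85)/5 = 0.0325, so P = 0.155.
- Odds ratio = (0.155/0.845)/(0.165/0.835) = 0.93 from unrounded values, although the hazard ratio is 1.
- The standard error of the log odds ratio with 443 and 442 patients is about 0.18. The shift is ln(0.93)/0.18, or about −0.4 standard errors. The one-sided error is about Φ(−1.96 + 0.4), or 6%.

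**5. The same by simulation**

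The simulation used 3,000 trials of 885 patients per setting, the stated accrual, cut-off at 7.7 years, no true effect and unstratified tests. Loss is shown as experimental versus control at year 5.

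| Assumed 5-year survival | Loss | Log-rank error | Logistic error | Mean odds ratio |
|---|---|---|---|---|
| 80% | 5% v 5% | 2.7% | 2.4% | 0.998 |
| 80% | 15% v 5% | 2.4% | 7.0% | 0.928 |
| 85% | 5% v 5% | 2.7% | 2.8% | 1.001 |
| 85% | 15% v 5% | 2.0% | 5.6% | 0.922 |
| 90% | 5% v 5% | 2.7% | 2.6% | 1.004 |
| 90% | 15% v 5% | 1.8% | 4.4% | 0.933 |

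Monte Carlo error on a 2.5% rate is about 0.3 percentage points. In an extreme case of 30% versus 5%, logistic error is 12.8% to 22.2% and log-rank error 2.2% to 2.6%. The distortion favours whichever arm loses more patients, so reversing the imbalance reverses its direction.

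With equal 5% loss and the PFS hazard ratio of 0.708 borrowed for illustration, power is 59.7% (log-rank) against 59.1% (logistic) at 80% survival, 49.3% against 48.3% at 85%, and 34.9% against 34.1% at 90%.

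**The case against.** The best defence is that this is a drafting slip. The primary endpoint and every other event-time endpoint in the same paragraph get a time-to-event model, so the authors probably meant Cox regression for overall survival too. The text at hand is also a summary: it refers to chapter 6.1.1.1 and to appendices that are not shown, so a fuller body exists and may name the method. Both points are fair. They limit the finding to what the summary says, and do not show that overall survival will in fact be analysed by logistic regression. They do not change what the clause says.

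The second defence is that little harm follows on the protocol's own figures. That stands. The only loss rate given is 5% at year 5, with no difference between arms, and under it the logistic test keeps its level and nearly all its power. A hazard ratio of 0.80 would appear as an odds ratio of about 0.78 to 0.79, which is a different effect measure and not a bias. Coding censored patients as survivors is also an inference: it follows from a death yes/no outcome without a landmark, but the protocol does not spell out the coding.

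A reader might extend the criticism to the other two items caught by the clause. The document does not support that. PSA six months after radiotherapy is not said to be continuous or dichotomised, and a threshold, for which logistic regression would be valid, could be left to the analysis plan. Switching is worded as a one-arm proportion, so it need not be read as a planned two-arm model.

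**Conclusion.** The clause is wrong as written for two endpoints: overall survival, because it is right-censored with unequal follow-up and no landmark, and total duration on the allocated drug, because it is not binary. Severity is moderate. Overall survival is a secondary endpoint with no stated power, and the superiority and non-inferiority tests on progression-free survival use stratified Cox regression and are untouched.

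A reader might infer that the planned overall survival result is materially biased. The documents do not support that. An odds ratio of 0.92 to 0.93 under no effect, with one-sided error of about 4% to 7%, needs an assumed 15% versus 5% loss imbalance, together with assumed 5-year survival of 80% to 90% and independent exponential censoring. With equal 5% loss the error is 2.4% to 2.8%. What the documents do support is that the stated method is exposed to unequal loss while the Cox or log-rank analysis is not, provided censoring is non-informative.

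**What to change.** - Add overall survival to the stratified Cox sentence, in the intention-to-treat population already set for secondary efficacy endpoints, with Kaplan-Meier curves.
- Restrict the logistic sentence to binary endpoints and list them by name, so that no endpoint is assigned by default.
- Analyse duration on the allocated drug with a time-to-event method that separates completion of the pre-elected 18, 24 or 36 months from early stopping. Without that separation, planned completion would count as discontinuation.
- Report switching from antagonist to agonist descriptively in the antagonist arm.
- If the protocol body already gives overall survival a time-to-event method, bring the summary into line with it.

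The cost is wording in the protocol, carried into the analysis plan. Sample size, data collection and the primary analysis do not change. The change should be made before overall survival is analysed.
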